#### 8.3.5 ADVERSE EVENT REPORTING

Non-serious AE will be recorded in the study database and will be summarized (by treatment arm) in safety reports for the DSMB to discuss at regular meetings.

#### 8.3.6 SERIOUS ADVERSE EVENT REPORTING

The study clinician will immediately report to the sponsor (University of Pittsburgh) any serious adverse event, whether or not considered study intervention related, including those listed in the protocol or investigator brochure and must include an assessment of whether there is a reasonable possibility that the study intervention caused the event. Study endpoints that are serious adverse events (e.g., all-cause mortality) must be reported in accordance with the protocol unless there is evidence suggesting a causal relationship between the study intervention and the event (e.g., death from anaphylaxis). In that case, the investigator must immediately report the event to the sponsor.

All serious adverse events (SAEs) will be followed until satisfactory resolution or until the site investigator deems the event to be chronic or the participant is stable. Other supporting documentation of the event may be requested by the Data Coordinating Center (DCC)/study sponsor and should be provided as soon as possible.

#### 8.3.7 REPORTING EVENTS TO PARTICIPANTS

Not applicable.

#### 8.3.8 EVENTS OF SPECIAL INTEREST

Not Applicable.

#### 8.3.9 REPORTING OF PREGNANCY

If a participant becomes pregnant or decides to try and get pregnant during the study (i.e. changes their mind or has an unplanned pregnancy), the participant should inform the local trial staff and local site PI immediately. Since this is one of the main exclusion criteria, these participants would then drop out of the study.

### 8.4 UNANTICIPATED PROBLEMS

#### 8.4.1 DEFINITION OF UNANTICIPATED PROBLEMS (UP)

The Office for Human Research Protections (OHRP) considers unanticipated problems involving risks to participants or others to include, in general, any incident, experience, or outcome that meets all of the following criteria:

- Unexpected in terms of nature, severity, or frequency given (a) the research procedures that are described in the protocol-related documents, such as the Institutional Review Board (IRB)-approved research protocol and informed consent document; and (b) the characteristics of the participant population being studied;
- Related or possibly related to participation in the research (“possibly related” means there is a reasonable possibility that the incident, experience, or outcome may have been caused by the procedures involved in the research); and
- Suggests that the research places participants or others at a greater risk of harm (including physical, psychological, economic, or social harm) than was previously known or recognized.

---

#### 8.4.2 UNANTICIPATED PROBLEM REPORTING

The investigator will report unanticipated problems (UPs) to the reviewing Institutional Review Board (IRB) and to the Data Coordinating Center (DCC)/lead principal investigator (PI). The UP report will include the following information:

- Protocol identifying information: protocol title and number, PI’s name, and the IRB project number;
- A detailed description of the event, incident, experience, or outcome;
- An explanation of the basis for determining that the event, incident, experience, or outcome represents an UP;
- A description of any changes to the protocol or other corrective actions that have been taken or are proposed in response to the UP.

To satisfy the requirement for prompt reporting, UPs will be reported using the following timeline:

- UPs that are serious adverse events (SAEs) will be reported to the IRB and to the DCC/study sponsor within 7 business days of the investigator becoming aware of the event.
- Any other UP will be reported to the IRB and to the DCC/study sponsor within 10 days of the investigator becoming aware of the problem.
- All UPs should be reported to appropriate institutional officials (as required by an institution’s written reporting procedures), the supporting agency head (or designee), and the Office for Human Research Protections (OHRP) within 10 days of the IRB’s receipt of the report of the problem from the investigator.

---

#### 8.4.3 REPORTING UNANTICIPATED PROBLEMS TO PARTICIPANTS

Not Applicable.

## 9 STATISTICAL CONSIDERATIONS

### 9.1 STATISTICAL HYPOTHESES

Null hypothesis: % Time-in-serious hypoglycemia and % Time in Range (TIR) in the insulin glargine group is the same as % Time-in-serious hypoglycemia and % TIR in the control group (usual care with human insulin).

Alternative hypothesis: % Time-in-serious hypoglycemia or % TIR in the insulin glargine group is different than in the control group (usual care with human insulin).

Since this trial has 2 coprimary outcomes, a win on either outcome will be considered to be a positive trial. For example, if insulin glargine “wins” ( $p<0.025$  for benefit) on either the Time-in-serious hypoglycemia OR TIR outcome, it’s considered a positive trial for analogue insulin.

## 9.2 SAMPLE SIZE DETERMINATION

We estimated power using a bootstrap-resampling approach due to the expected non-standard distribution of the outcome variables (i.e. %time in serious hypoglycemia and %time-in-range). Using individual patient level CGM data collected from a pilot study involving more than 80 children with T1D in Uganda and Kenya (personal communication [name], University of Minnesota), we calculated a mean percent time $<54$  mg/dl of 5.8, standard deviation of 6.6, a maximum of 24. We next assumed a clinically meaningful 33% relative reduction in percent time-in-serious-hypoglycemia (e.g., from a median of 6% to 4%) since clinical guidelines recommend that patients and providers aim for <15 minutes per day (~1%) in hypoglycemia spent at <54 mg/dl. Therefore, in each simulated trial, the simulated patients in the usual-care arm had an outcome drawn from the “control” distribution; the simulated patients in the glargine arm had an outcome drawn from the control distribution multiplied by 0.67 (e.g. corresponding to a 33% relative reduction in time-in-serious-hypoglycemia).

To estimate the study power, we simulated outcomes for control-group (human insulin) and treatment-group (analogue insulin) at sample sizes ranging from 100 up to 400 patients and performed the planned primary analyses described above on the simulated datasets. The power to detect a treatment benefit of glargine insulin is thereby computed as the percentage of simulated trials with a p-value less than 0.025 favoring glargine on each of the respective coprimary outcomes. Since we have 2 coprimary outcomes, an alpha threshold of 0.025 is used for each analysis to control the overall trial-wide type 1 error probability at 0.05. Using this approach, an analytic sample size of 300 patients (150 per arm) would have 77.7% power to detect a treatment benefit corresponding to approximately a 33% relative reduction in time-in-serious-hypoglycemia. If the benefit is larger (e.g. 50% relative reduction) we will have over 99% power to detect a treatment benefit on the hypoglycemia endpoint.

For the time-in-range endpoint, we used an absolute increase rather than a relative decrease; this is because of the different distribution of time-in-range as opposed to time-in-serious-hypoglycemia (which has a large clustering of values in single digits). The pilot data showed a mean time-in-range of 27 with a standard deviation of 17; most values ranged between about 10 and 70; we felt that a 10% absolute increase in time-in-range would be a clinically meaningful improvement. Using a similar resampling-based approach described above, for this endpoint simulated patients in the usual care arm had an outcome drawn from the “control” distribution; simulated patients in the analogue arm had an outcome drawn from the control distribution plus 10 (corresponding to a 10% absolute increase in the time-in-range endpoint). The planned sample size of N=300 retains excellent power (>99%) for a 10% absolute improvement in time-in-range.

**Table.** Power For “%Time<54mg/dl” and “%Time-In-Range” Outcomes At Various Sample Sizes (alpha=0.025)

Sample Size	%Time<54mg/dl		%Time-In-Range
	33% Relative Decrease	50% Relative Decrease	10% Absolute Increase
N=200	56.2%	96.6%	97.5%
N=250	64.3%	99.0%	99.5%
N=300	77.7%	99.8%	>99.9%

Therefore, we believe that a sample size of N=300 patients (150 per group) with analyzable outcome data will be sufficient to have sufficient power for clinically relevant effects on the co-primary outcomes of time-in-serious-hypoglycemia (77.7% power to detect a 33% relative decrease at alpha=0.025) and time-in-range (>99% power to detect a 10% absolute increase at alpha=0.025). This analytic strategy allows the trial to conclude as a positive trial if glargine demonstrates a benefit on either the time-in-serious-hypoglycemia endpoint or the time-in-range endpoint. Splitting the alpha to use 0.025 for each coprimary endpoint controls the overall trial-wide error at 0.05; this gives the opportunity to test both endpoints, which is important as knowledge of a benefit on either aspect of glycemic control is useful to inform clinical practice.

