## 7 STUDY INTERVENTION DISCONTINUATION AND PARTICIPANT DISCONTINUATION/WITHDRAWAL

### 7.1 DISCONTINUATION OF STUDY INTERVENTION

Discontinuation from the study intervention does not mean discontinuation from the study, and remaining study procedures should be completed as indicated by the study protocol. For example, a participant may decide that they would like to go back to their previously used human insulin regimen. During the study, participants will be encouraged to stay on their randomly assigned treatment group, unless there is a clinical reason to switch (i.e. cross-over).

At the end of this study, participants will be given the opportunity to switch to the contralateral treatment group if they would like to (and the treating provider agrees).

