#### 9.4.2 ANALYSIS OF THE PRIMARY EFFICACY ENDPOINT(S)

The trial will have coprimary outcomes. The first of these will be percent time-in-serious-hypoglycemia (<54 mg/dl) as described above, which will be recorded as a continuous variable theoretically ranging from 0 (no time spent in serious hypoglycemia) to 100 (all time spent in serious hypoglycemia); the realistic range for this outcome is ~0 to 25, as described below. Data on percent time in hypoglycemia will be downloaded from individual CGM sensors and then pooled across both sensors collected during the intensive CGM phase (month +6 to +7) to compute a single value for “time in serious hypoglycemia” for each patient. The primary analysis will be performed using a multivariable linear regression model where treatment assignment is the primary fixed effect of interest, with age, study site, and time-in-serious-hypoglycemia and time-in-range from the baseline CGM (run-in phase, prior to initiation of study treatment) included as covariates. This approach will be used because adjustment for covariates known to be strongly associated with the outcome increases statistical power; including the baseline measurement as a covariate also provides a safeguard against random imbalances in individual level baseline risk of hypoglycemia (e.g. one arm having patients with more hypoglycemic tendencies than the other arm) introducing a bias in the estimated treatment effect.

The second coprimary outcome will be percent time-in-range (70-180 mg/dl). Likewise, this also will be recorded as a continuous variable theoretically ranging from 0 (no time spent in range) to 100 (all time spent in range). The realistic range for this outcome variable is about 10 to 70, based on pilot data also

described below. Again, data from all CGM sensors collected during the intensive CGM phase (month +6 to +7) will be pooled to compute a single value for “time in range” for each patient. The analytic approach used for this endpoint will mirror the approach used for the time-in-serious-hypoglycemia endpoint: a multivariable linear regression model where treatment assignment is the primary fixed effect of interest, with age, study site, and time-in-range from the baseline CGM (run-in phase, prior to initiation of study treatment) included as covariates.

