**Incomplete or missing CGM Sensor Data:** Even though returning a baseline CGM sensor (i.e. the one placed during the run-in phase) is one of the trial eligibility criteria, it is expected that some participants may have incomplete or missing CGM sensor data. For example, a CGM sensor could fall off accidentally before the end of each 14 day sensor wear period. Such sensors may also be lost before study staff have an opportunity to download the glucose data.

If a CGM sensor falls off early, or presents with no data due to a sensor download error, or is accidentally removed less than 9.8 days (70% of 14 days; consistent with international consensus recommendations on the use of CGMs in clinical trials), they may receive a replacement sensor. If a participant is able to successfully wear a sensor for 14 days, but a sensor shuts-off early (e.g. only 6 days of glucose measurement data is captured), they will not have a replacement sensor. Rationale: randomization should balance incomplete sensor data across the two study arms.

In the *primary* analysis, we will include all available sensor data (regardless of the duration of sensor wear or the number of days of glucose measurements) collected while enrolled in the study. In a *sensitivity* analysis, we will include only sensors with at least 70% of data availability during each 14 day wear period (i.e.  $\geq 9.8$  days). In another *sensitivity* analysis, we will impute for missing data. In an exploratory analysis, we will include data from 12-month follow-up replacement sensors that were collected after a participant completed study.

**Lost to follow-up:** If a participant discontinues before any of the follow-up CGM data are recorded (e.g. participant has no recorded CGM data at all during follow-up) they will not contribute data to the primary efficacy analysis. As described above, we are planning the study to have sufficient power with a usable analytic sample of  $n=300$  participants. We propose to recruit  $n=400$  participants, which allows for up to 25% attrition (participants that are lost shortly after randomization, before any CGM data have been collected) while retaining sufficient power to test our primary hypothesis.

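### The fixed 0.025 split is valid but leaves alpha unused once one co-primary is won; a Holm step could add up to about 8 points of hypoglycemia power in the combined planning scenario, depending on the time-in-range (TIR) result and on baseline adjustment

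*Combined protocol and SAP*

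**What the plan says.** Section 9.1 defines success as a win on either co-primary: "a win on either outcome will be considered to be a positive trial". The alternative hypothesis is two-sided (a difference), and a win means p<0.025 in favour of glargine.

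Section 9.2 explains the threshold: "an alpha threshold of 0.025 is used for each analysis to control the overall trial-wide type 1 error probability at 0.05", and again "Splitting the alpha to use 0.025 for each coprimary endpoint controls the overall trial-wide error at 0.05". It tests both endpoints because "knowledge of a benefit on either aspect of glycemic control is useful to inform clinical practice".

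The stated power with 300 analysed is 77.7% for a 33% relative reduction in time below 54 mg/dl, and above 99% for a 10-point rise in TIR. Each figure comes from its own simulation of one endpoint, and 77.7% is already labelled as power at alpha 0.025. Section 9.2 says that the simulations "performed the planned primary analyses described above on the simulated datasets".

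Section 9.4.2 gives a regression model for each endpoint but no rule for passing alpha from one to the other. Section 9.4.1 (General Approach) is marked as not applicable.

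**The concern.** A fixed split spends 0.025 on each endpoint whatever happens on the other. Once one null hypothesis has been rejected, only one remains, and it can be tested at the full 0.05 without raising the family-wise error above 0.05. The plan has one very strong endpoint on its own assumptions (TIR) and one below 80% power (hypoglycemia), which is where such a step helps most.

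At stake is which benefits can be claimed, not whether the trial is positive. If TIR is won and hypoglycemia gives a p-value between 0.025 and 0.05 in favour of glargine, the current rule cannot claim the hypoglycemia benefit and a Holm rule can. Section 9.2 values knowledge of a benefit on either aspect of control, so the question is relevant, although the plan sets no goal of winning both.

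**Working it through.** **Inputs (section 9.2).** Control time below 54 mg/dl: mean 5.8, SD 6.6. Glargine outcome = control × 0.67, so the difference is 0.33 × 5.8 = 1.914 and the glargine SD is 0.67 × 6.6 = 4.422. TIR: SD 17, effect +10. 150 analysed per arm. Critical values: 2.241 (two-sided 0.025) and 1.960 (two-sided 0.05).

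**Step 1: the plan's own figures.**
- Hypoglycemia: SE = √((6.6² + 4.422²)/150) = 0.6487; z = 1.914/0.6487 = 2.951. Power at 0.025 = Φ(2.951 − 2.241) = 76.1%, against the stated 77.7%. t-tests on skewed distributions with the same mean and SD give 76.4-77.6%.
- TIR: z = 10/(17 × √(2/150)) = 5.09; power 99.8%, against the stated >99.9%.
- A one-sided 0.025 test would give 83.9% for hypoglycemia, so the plan's figure fits a two-sided 0.025.

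**Step 2: the Holm step.** At two-sided 0.05, hypoglycemia power is Φ(2.951 − 1.960) = 83.9%. The chance of a p-value between 0.025 and 0.05 for benefit is therefore 83.9% − 76.1% = 7.8%. That band can be claimed only if TIR has been won at 0.025. With independent test statistics, gain = 7.8% × P(TIR won).

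| True TIR effect | TIR z | P(TIR won at 0.025) | Gain in hypoglycemia power | Positive trial, either rule |
|---|---|---|---|---|
| +10 | 5.09 | 99.8% | 7.8 points | 99.95% |
| +5 | 2.55 | 62.0% | 4.8 points (4.9 simulated) | 90.9% |
| +3 | 1.53 | 23.8% | 1.9 points | 81.8% |
| 0 | 0 | 1.25% | 0.1 point | 76.4% |

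The last column cannot differ between the rules, because the first win is at 0.025 under both. The skewed t-test simulations with TIR +10 give 84.4-85.3% under Holm. Correlation between the endpoints barely matters at TIR +10; at +5, correlations of −0.3 to 0.3 give Holm power of 80.2-81.7%. At TIR +5 the step also helps TIR itself, from 62.0% to 69.7%.

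**Step 3: baseline adjustment.** The planned model adjusts for baseline CGM, because "adjustment for covariates known to be strongly associated with the outcome increases statistical power". The documents give no baseline-outcome correlation r, so r is an assumption. Adjustment multiplies the SE by √(1 − r²). With TIR +10:

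| Assumed r | z, N=300 | Gain, N=300 | z, N=400 | Gain, N=400 |
|---|---|---|---|---|
| 0 | 2.951 | 7.8 | 3.407 | 4.8 |
| 0.3 | 3.093 | 6.9 | 3.572 | 3.8 |
| 0.5 | 3.407 | 4.8 | 3.934 | 2.1 |
| 0.7 | 4.132 | 1.4 | 4.771 | 0.3 |

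N=300 is what remains of 400 after the full attrition allowance ("which allows for up to 25% attrition"), so the right-hand columns show the case of no loss.

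**Step 4: other hypoglycemia effects** (N=300, unadjusted, TIR +10). A 25% reduction gains 11.2 points (46.5% to 57.6%), about the maximum; 40% gains 3.2; 50% gains 0.3.

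**Step 5: error control.** The rule rejects nothing that ordinary Holm would not, so the two-sided error is at most 0.05 under any correlation. Simulation with equal second-step thresholds for benefit and harm gave, across correlations −0.9 to 0.9, 0.036-0.050 under the global null, 0.050 with hypoglycemia null and TIR +10, and 0.037-0.044 with TIR null and a 33% hypoglycemia reduction. False benefit claims were about 0.025 or less throughout.

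**Step 6: what the extra claims look like** (N=300, unadjusted). They rest on observed differences from 1.960 × 0.6487 = 1.27 to 2.241 × 0.6487 = 1.45 points. Divided by 5.8, these are reductions of 21.9% to 25.1%. For a difference of 1.36, the 97.5% interval is −0.09 to 2.81 and the 95% interval is 0.09 to 2.63.

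**The case against.** The strongest reply is that this is a preference. The sponsor chose a valid and simple split, gave its reason, and defined success as a win on either endpoint; the chance of that success does not move. This stands, and it is why the point is optional.

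The second reply is that the headline gain comes from a favourable corner: both planned effects true at once, no covariate adjustment, and the smallest planned sample. This also stands. A reader might infer that the plan's own scenario gives 84% power under Holm. The plan never assumes a 33% reduction and TIR +10 together; that combination is made here. Nor is +10 assured, since section 6.1.2 does not recommend aggressive lowering of fasting glucose or HbA1c. The gain should be quoted as a range.

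Third, the added claims are the weakest ones: reductions of about 22-25%, below the 33% that section 9.2 treats as clinically meaningful. True, but the current rule already accepts results from about 25%.

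Fourth, one could relax the threshold for benefit only and keep harm at 0.025. Hypoglycemia is also a safety outcome (sections 8.2 and 9.4.4), so that would make benefit easier to declare than harm. It is also unnecessary, because symmetric testing already keeps the error at 0.05.

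Fifth, loosening a primary threshold in an open-label trial under way invites suspicion. That is a real cost, handled by the condition on timing below.

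**Conclusion.** The point holds as an optional improvement. The fixed split is valid but not fully efficient. With both planned effects true, 300 analysed and no adjustment, a Holm step raises hypoglycemia power from about 76-78% to about 84-85%. The gain falls to 0.1 point if TIR does not change, and to 1.4 points (N=300) or 0.3 (N=400) at an assumed baseline-outcome correlation of 0.7.

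Two stronger readings are not supported. One is that the split fails to control error: it is a Bonferroni split and holds under any correlation. The other is that Holm would make a positive trial more likely: that probability is identical under both rules.

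The figures rest on the pilot means and SDs in section 9.2, normal test statistics checked against skewed simulations, and zero correlation between endpoints unless stated.

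**What to change.** In 9.1, 9.2 and 9.4.2, state that:
- a co-primary is won at two-sided p<0.025 in the direction of benefit for glargine;
- once one is won, the other is tested at two-sided p<0.05, with the same threshold for benefit and for harm;
- if neither is won, both stay at 0.025.

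Beside the existing 77.7%, give the Holm power and say that it depends on winning TIR. Report 97.5% intervals for both endpoints, and add a 95% interval, labelled as not simultaneous, for an endpoint claimed at the 0.05 step.

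**Cost.** No patients, visits or data are added. The change needs an IRB-approved amendment (Statement of Compliance) in a trial that is under way: section 6.1.2 describes a January 2024 supply change in the past tense. Intervals become harder to present, because an endpoint claimed at the second step has a 97.5% interval that includes zero. At N=300 unadjusted, the smallest claimable hypoglycemia reduction falls from about 25% to about 22%.

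**Condition.** Date the amendment before those deciding it have seen outcome data by arm, and record which data flows they could access: clinician alerts for sensors above 10% (8.2), adverse events by arm to the DSMB (8.3.5), the six-monthly committee review (10.1.6), and the regular data review (10.1.7, which does not say whether it is by arm). No efficacy interim is planned (9.4.6), and the documents do not show that anyone deciding has seen such results. If they have, keep the current rule.
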